--	--

	
of contraception (failure rate < 1% per year) with their male partners during treatment and for 6 months following the last study drug dose.
 
No waivers of these inclusion or exclusion criteria will be granted by the investigator and the sponsor or its designee for any patient enrolled into the study.

Study Treatment	
Eligible patients will be randomized 2:1 to receive rucaparib (600 mg twice a day [BID]) or placebo. Randomization will occur by a central randomization procedure using an Interactive Voice Response System/Interactive Web Response System (IVRS/IWRS). The following will be included as randomization stratification factors at study entry to ensure treatment groups are balanced:
 
 
• HRD classification (tBRCA, nbHRD, or biomarker negative) by the ICTA (Appendix A).
 
• Interval between completion of the penultimate platinum-based regimen and disease progression (6 to 12 or >12 months) by radiologic assessment
 
• Best response to the most recent platinum-based regimen (CR [defined as complete radiologic response by RECIST or PR [defined as partial response by RECIST and/or a GCIG CA-125 response]). All responses require that CA-125 be <ULN.
 
 
Randomization to study treatment must occur within 8 weeks following a patient's last dose of platinum-based chemotherapy. Study drug will be taken orally twice daily (12 hours apart) with at least 8 oz (240 mL) of water. Study drug may be taken with an empty stomach or with food.
 
Patients will take study drug twice daily for continuous 28-day cycles until disease progression by RECIST as assessed by the investigator, or other reason for discontinuation. Treatment interruptions and/or dose reductions are permitted in the event of unacceptable toxicity.

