3 GENERAL ANALYSIS CONVENTIONS

The summary tables will be presented by randomized treatment group (rucaparib vs placebo) within the nested populations outlined in the step-down procedure in Section 3.2 and other subgroups of interest.

Quantitative variables will typically be summarized using frequencies and percentages for appropriate categorizations and may also be summarized using descriptive statistics. For variables summarized with descriptive statistics, the following will be presented: N, mean, standard deviation, median, minimum, and maximum. Categorical variables will be presented using frequencies and percentages. The Kaplan-Meier methodology will be used to summarize time-to-event variables. If estimable, the 25th, 50th (median), and 75th percentiles will be presented along with the Kaplan-Meier estimates of event rates at 6-month intervals. The number of patients with events and the number of censored patients will also be presented. The stratified log rank test will be used to compare the PFS distributions between the randomized treatment groups. In addition, the Cox proportional hazards model will be used to estimate the hazard ratio between the randomized treatment groups. Months will be calculated as number of days divided by 30.4375.

All data will be used to their maximum possible extent, but without any imputations for missing data.

Unless otherwise indicated, baseline is defined as the last measurement on or prior to randomization.

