12.1 Adverse Events

AEs will be classified using the MedDRA version 19.1 classification system. The severity of the toxicities will be graded according to the National Cancer Institute Common Terminology Criteria for Adverse Events (NCI CTCAE) whenever possible. Treatment-emergent adverse events (TEAEs) are defined as AEs with onset date on or after the date of first dose of study medication until the date of the last study medication dose plus 28 days. AEs will be considered treatment-emergent if all or part of the date of onset of the adverse event is missing and it cannot be determined if the AE meets the definition for treatment-emergent.

The number and percentage of patients who experienced TEAEs for each SOC and PT will be presented. Multiple instances of the TEAE in each SOC and multiple occurrences of the same PT are counted only once per patient. The number and percentage of patients with at least one TEAE will also be summarized.

Separate tables will be presented as follows:

- All TEAEs;
- TEAEs by CTCAE grade;
- Grade 3 or greater TEAEs;
- Treatment-related TEAEs;
- Serious TEAEs;
- TEAEs with an outcome of death;
- TEAEs leading to discontinuation of study medication;
- TEAEs resulting in reduction study medication;
- TEAEs resulting in interruption of study medication;
- TEAEs resulting in reduction or interruption of study medication;
- Time to the first TEAE that results in a reduction or interruption of study drug.

The incidence of TEAEs will be summarized by relationship to study drug according to the following categories: "treatment-related," or "not treatment-related". If a patient experiences multiple occurrences of the same AE with different relationship categories, the patient will be counted once, as a relationship category of treatment related.

If a patient experiences multiple occurrences of the same AE with different toxicity grades, the patient will be counted once for the maximum (most severe) toxicity grade. AEs with a missing toxicity grade will be presented in the summary table with a toxicity grade of "Missing." For each toxicity grade, the number and percentage of patients with at least one TEAE of the given maximum grade will be summarized.

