The time to the first TEAE and first treatment-related TEAE that results in a dose reduction, delay, interruption, or discontinuation of study drug is defined as 1+ the number of days from the first dose of study drug to the start of the first adverse event. The cumulative incidence is presented in a 1-KM graph for just the patients with an event and the median time to onset will be calculated together with the 95% CI.

Non-TEAEs (pre-treatment and post-treatment) will be presented in the by patient data listings for the safety population.

MedDRA PTs were combined for the following similar terms:

- Asthenia/Fatigue
- Alanine Aminotransferase (ALT)/ Aspartate Aminotransferase (AST) Increased
- Anaemia and/or Low/Decreased Haemoglobin
- Thromobocytopenia and/or Low/Decreased Platelets
- Neutropenia and/or Low/Decreased Absolute Neutrophil Count (ANC)

In addition, the analysis of combined terms for anemia is explored as a time to first event analysis as described above. Transfusions (blood or plasma) and concomitant medications / growth factor support are provided in patient listings. The number of transfusions and the time to fist transfusion is also summarized.

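### SAP 12.1 calls a 1-KM curve drawn only in patients with the event a cumulative incidence; it must end at 100% however few treated patients are affected

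*SAP*

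**What the plan says.** SAP section 12.1 defines the time to the first TEAE, and to the first treatment-related TEAE, that leads to a dose reduction, delay, interruption or discontinuation. The time "is defined as 1+ the number of days from the first dose of study drug to the start of the first adverse event". The display follows: "The cumulative incidence is presented in a 1-KM graph for just the patients with an event". A median onset time with a 95% confidence interval accompanies the graph. No censoring rule is given for patients without the event, because they are not in the analysis.

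The table list in the same section includes "Time to the first TEAE that results in a reduction or interruption of study drug". It also provides ordinary incidence: "The number and percentage of patients with at least one TEAE will also be summarized", with separate tables for TEAEs leading to discontinuation, reduction and interruption. Further on, "the analysis of combined terms for anemia is explored as a time to first event analysis as described above".

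SAP section 3 has summary tables presented by randomized arm. Section 12.1 does not say whether the graph is split by arm. Under the protocol synopsis, treatment runs in "continuous 28-day cycles until disease progression by RECIST as assessed by the investigator", or until another reason for stopping.

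**The concern.** Cumulative incidence at time t is the proportion of treated patients who have had the event by t. Patients who never have the event belong in the denominator; without them the quantity changes. The SAP states the restriction openly but keeps the name.

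A reader who takes the title at its word gets a wrong figure for tolerability. If the graph is drawn by arm, two arms with very different event frequencies can look alike or appear in the wrong order. The shape of an events-only curve also depends on how long patients stay on drug. That length is set largely by progression, so it may differ between arms. The displays affected are those for dose-modifying TEAEs, and the combined-term anemia analysis if the cross-reference there carries over the graph and not only the time definition.

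**Working it through.** **The part that needs no assumption.** Let n be the number of patients with the event. If only these n are analysed, every time is an observed event and none is censored. The Kaplan-Meier estimate is then the empirical survivor function, so

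1-KM(t) = (events by t) / n,

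which equals 1 at the last event. The SAP gives no figure of its own to reproduce, so this was run on simulated onset times with 360 and 180 treated patients (540 randomized 2:1, SAP section 2.3, taking all as treated). Assumed shares affected were 5%, 10%, 30% and 70%, that is 18, 36, 108 and 252 events, or 9, 18, 54 and 126. The events-only curve ended at 100% every time. In all treated patients, with those unaffected followed to day 365, the curve ended at 5%, 10%, 30% and 70%. The events-only median was always defined; the all-patient median was reached only at 70%.

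**Size of the distortion (illustrative).** Assumptions: exponential times; planning PFS medians from SAP section 2.3 as a proxy for time on drug (ITT 8.5 vs 6 months, tBRCA 12 vs 6); TEAE hazards h per month chosen by me, since the documents give none. With μ = ln 2 / median time on drug:

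- true incidence at t = h/(h+μ) × [1 − exp(−t(h+μ))]
- plotted events-only curve = 1 − exp(−t(h+μ))
- ever affected = h/(h+μ)

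Example 1 at t = 6:

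- Rucaparib: μ = 0.693/8.5 = 0.0815, h+μ = 0.1615. Plotted 1 − exp(−0.969) = 62.1%; ever affected 0.08/0.1615 = 49.5%; true 0.495 × 0.621 = 30.7%.
- Placebo: μ = 0.693/6 = 0.1155, h+μ = 0.1255. Plotted 1 − exp(−0.753) = 52.9%; ever affected 0.01/0.1255 = 8.0%; true 0.080 × 0.529 = 4.2%.

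About 178 of 360 and 14 of 180 patients are ever affected, and both curves end at 100%.

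| Example | Medians (months) | h, rucaparib vs placebo | True at 6 months | Plotted at 6 months |
|---|---|---|---|---|
| 1 | 8.5 vs 6 | 0.08 vs 0.01 | 30.7% vs 4.2% | 62.1% vs 52.9% |
| 2 | 8.5 vs 6 | 0.05 vs 0.01 | 20.7% vs 4.2% | 54.6% vs 52.9% |
| 3 | 8.5 vs 6 | 0.04 vs 0.02 | 17.0% vs 8.2% | 51.8% vs 55.7% |
| 4 | 12 vs 6 | 0.05 vs 0.01 | 22.1% vs 4.2% | 47.6% vs 52.9% |

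In examples 3 and 4 the arm with the higher incidence plots lower.

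**Adding the 28-day TEAE window.** With d = 28/30.4375 months and t > d,

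I(t) = (1 − exp(−hd)) + h·exp(μd)·[exp(−(h+μ)d) − exp(−(h+μ)t)]/(h+μ),

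and the plotted value is I(t)/I(∞). Example 1 becomes 32.85% vs 4.6% true and 61.9% vs 52.6% plotted. Example 3 becomes 18.2% vs 9.0% true and 51.6% vs 55.4% plotted, so the reversal stays. A simulation of 4,000,000 patients per arm agreed with the example 1 values.

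**Where the arm effect is small.** With equal hazards and ITT medians, the events-only median onset is ln 2/(h+μ). Underlying onset medians of 1, 3 and 12 months give 0.89 vs 0.86, 2.2 vs 2.0 and 5.0 vs 4.0 months. For early-onset events the dependence on time on drug hardly matters.

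**The case against.** The strongest reply is that this is a labelling slip disclosed in its own sentence. Read whole, the text describes onset timing among affected patients, which is a legitimate descriptive summary, and those patients are a declared subset of the safety population. Incidence is reported in the n (%) tables. The protocol's own AE tables (section 11.2.5.1) include no time-to-event display, so the graph is an extra.

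Much of this stands. The percentages do limit the harm, although the exact composite in the graph, with delay and discontinuation included, has no listed table of its own. The split by arm and the carry-over to anemia are not stated. The magnitudes rest on chosen hazards, and the reversals would be hard to see in data: example 3 expects about 118 and 27 events, and its 3.9-point gap has a standard error of about 10.7 points. Example 4, in a tBRCA group of minimum size (180, hence 60 on placebo), expects about 5 placebo events. The protocol also describes transaminase rises as early, the case in which the arm effect is negligible, though it says myelosuppression may be delayed.

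The Aalen-Johansen curve also depends on time on treatment: with equal hazards of 0.02 and ITT medians it plateaus at 19.7% vs 14.8%. But it does estimate the share of treated patients affected by time t. The events-only curve does not, and a disclosure in the SAP puts no caveat on the figure.

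**Conclusion.** The concern holds. The endpoint of 100% follows by algebra for any number of events, so the graph as specified cannot show cumulative incidence, whether pooled or by arm. The size of the misreading depends on event rates the documents do not give. In the illustrations a true contrast of 30.7% vs 4.2% is drawn as 62.1% vs 52.9%, and one of 17.0% vs 8.2% is drawn in the wrong order. Those figures rest on constant hazards and on PFS medians as a proxy for time on drug. The consequence is confined to descriptive safety displays; no hypothesis test, alpha or efficacy result is affected. It should be corrected but does not threaten the trial's conclusions.

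**What to change.** Preferred: draw the curve in all safety-population patients, by arm, as an Aalen-Johansen cumulative incidence. Treat the end of the TEAE window (last dose plus 28 days) or death without the event as the competing event, and censor administratively at the data cut-off. State whether the same display applies to the combined anemia terms.

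A 1-KM curve in all treated patients, censored at last dose plus 28 days, may be added if it is labelled as a separate on-treatment quantity. It is not a substitute: in example 1 it gives 1 − exp(−0.08 × 6) = 38.1% against the windowed incidence of 32.85%, a difference of 5.3 points.

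Keep the events-only median as time to onset among patients with the event, and do not use it to compare arms.

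Minimum: retitle the existing graph in the same words. This corrects the label but leaves no display of incidence over time.

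Cost: a short SAP edit and a small programming change, or wording alone for the minimum. The onset, dosing and death dates are already needed for other planned analyses.

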### **5.1.5 Follow-Up Phase**

[figure not shown]
After the Treatment Discontinuation visit, all patients will be followed for AEs up to 28 days after last dose of study drug. All serious adverse events (SAEs) and AESIs are to be followed to resolution, stabilization, or lost to follow-up (refer to [Section 10.7](#)) even if the duration extends beyond the 28-day follow-up period. Patients will also be followed for survival, subsequent treatments, and monitoring for secondary malignancy approximately every 12 weeks ( $\pm$  14 days) until death, loss to follow-up, withdrawal of consent, or study closure.

Patients who discontinued treatment for reason other than disease progression or death should continue to have tumor scans performed at 12 week intervals from Cycle 1 Day 1 (a window of up to 7 days prior is permitted) until disease progression by RECIST v1.1, as assessed by the investigator, or death. Patients who have been on study at least 18 months may decrease the frequency of disease assessments to every 16 ( $\pm$ 2) weeks. Investigator should consult with sponsor's medical monitor before decreasing frequency.

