- h All patients discontinued from treatment, regardless of reason, should be followed for subsequent treatments, secondary malignancy, and survival approximately every 12 weeks ( $\pm 14$  days) from Cycle 1 Day 1 until death, loss to follow-up, withdrawal of consent from study, or closure of the study. Follow-up can be performed via the telephone. Diagnosis of any secondary malignancy requires appropriate documentation (i.e., laboratory and/or pathology reports) and should be reported as specified in [Section 10](#).

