#### **9.4.3 Long-term Follow-up**

- Disease assessment for patients who discontinued treatment for reason other than disease progression or death. Tumor scans should continue to be performed at 12-week intervals (up to 7 days prior permitted) until radiologic disease progression by RECIST v1.1, as assessed by the investigator. Patients who have been on study at least 18 months may decrease the frequency of disease assessments to every 16 ( $\pm 2$ ) weeks. Investigator should consult with sponsor's medical monitor before decreasing frequency.
- Subsequent treatments, secondary malignancy monitoring, and OS information will be collected for all patients approximately every 12 weeks ( $\pm 14$  days) until death, loss to follow-up, withdrawal of consent from study, or closure of the study. Follow-up can be performed via the telephone. Diagnosis of any secondary malignancy requires appropriate documentation (i.e., laboratory and/or pathology reports) and should be reported as indicated in [Section 10.8](#).

- SAEs related to study drug and all AESIs, irrespective of causality, are to be reported as specified in [Section 10.8](#).

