### **9.5.4 Safety Evaluations**

#### **9.5.4.1 Adverse Event Assessment**

The investigator is responsible for assessing the safety of the patients and for compliance with the protocol to ensure study integrity. Patients will be monitored for AEs during study participation, beginning after the first dose of study drug and until 28 days after the last dose of study drug. Any ongoing SAEs and AESIs will be recorded and followed until resolution, stabilization, or loss to follow-up. Only treatment-related SAEs and all AESIs, regardless of causality, need to be reported after the 28-day window. SAEs will be graded according to the NCI-CTCAE grading system (v4.03) and recorded on the eCRF.

Complete details for monitoring AEs, including the definition of drug-related AEs, are provided in [Section 10](#).

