## **10.7 Recording of Adverse Events, Serious Adverse Events, and Adverse Events of Special Interest**

As of the implementation of Amendment 5, only SAEs/AESIs will be fully documented on the appropriate eCRF. For each SAE/AESI, the investigator must provide duration (start and end dates or ongoing), intensity, relationship to study drug, and indicate whether specific action or therapy was required.

Any SAE/AESI that occurs after the first dose of study drug until 28 days after last dose of study drug administration will be collected, documented and reported to the sponsor by the investigator according to the specific definitions and instructions detailed within this protocol, whether dosing has occurred or not. In addition, any AE/SAE that occurs after informed consent is obtained and is deemed related to a screening procedure for the study should also be reported on the AE eCRF and, if applicable, the SAE report form. Events that occur after signing of informed consent but prior to initiation of study drug, unless due to a protocol-mandated procedure, should be recorded on the Medical History eCRF. In order to avoid vague, ambiguous, or colloquial expressions, the AE should be recorded in standard medical terminology rather than the patient's own words. Whenever possible, the investigator should combine signs and symptoms that

constitute a single disease entity or syndrome into a final diagnosis. For example, fever, cough, and shortness of breath may be reported as pneumonia, if that is a reasonable diagnosis.

All SAEs/AESIs that occur during the study or within 28 days after receiving the last dose of study drug, regardless of relationship to study drug, must be reported to the sponsor/designated safety contact immediately (i.e., within 24 hours of the investigator's knowledge of the event). This should be done by faxing or emailing the completed SAE/AESI report to the sponsor/designee contact provided on the SAE/AESI report form. After the 28-day window after treatment discontinuation, only SAEs assessed as related to study drug and all AESIs, irrespective of causality, should be reported. If a patient is determined to be a screen failure, no further AEs/SAEs are required to be reported once that determination has been made, with the exception of AEs/SAEs deemed related to a protocol-specified procedure. Information on the follow-up of AEs, SAEs, and AESIs is provided in [Section 10.7.4](#).

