#### **11.2.5.1 Adverse Events**

AEs will be classified using the Medical Dictionary for Drug Regulatory Activities (MedDRA) classification system. The severity of the toxicities will be graded according to the NCI-CTCAE whenever possible. Only treatment-emergent adverse events (TEAEs) will be collected: TEAEs are defined as AEs with onset date on or after the date of first dose of study medication until the date of the last study medication dose plus 28 days.

The number and percentage of patients who experienced TEAEs for each system organ class (SOC) and preferred term will be presented. Multiple instances of the TEAE in each SOC and multiple occurrences of the same preferred term are counted only once per patient. The number and percentage of patients with at least one TEAE will also be summarized.

Separate tables will be presented as follows:

- All TEAEs
- TEAEs by CTCAE grade
- Grade 3 or greater TEAEs
- Serious TEAEs
- TEAEs with an outcome of death
- TEAEs leading to discontinuation of study medication
- TEAEs resulting in interruption/delay of study medication
- TEAEs resulting in dose reduction of study medication

If a patient experiences multiple occurrences of the same AE with different toxicity grades, the patient will be counted once for the maximum (most severe) toxicity grade. AEs with a missing toxicity grade will be presented in the summary table with a toxicity grade of "Missing." For each toxicity grade, the number and percentage of patients with at least one TEAE of the given grade will be summarized.

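### Secondary malignancies and special-interest events arising more than 28 days after last dose are followed or reportable, but no planned adverse-event table counts them by arm

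*SAP*

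**What the plan says.** **What is gathered after treatment.** Protocol 5.1.5 states: "Patients will also be followed for survival, subsequent treatments, and monitoring for secondary malignancy approximately every 12 weeks", and this continues "until death, loss to follow-up, withdrawal of consent, or study closure". Table 3 (footnote h) and section 9.4.3 repeat the rule and ask for laboratory or pathology documentation of any diagnosis. For AESIs, section 9.5.4.1 states: "Only treatment-related SAEs and all AESIs, regardless of causality, need to be reported after the 28-day window". Sections 9.4.3, 10.7 and 10.8 agree. After Amendment 5 reduced data entry, section 13.6 still keeps the forms for SAEs/AESIs, subsequent anticancer therapy and long-term follow-up.

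**What is tabulated.** SAP 12.1 closes the treatment-emergent (TEAE) window 28 days after last dose, and each adverse-event table it lists is a TEAE table. Of the rest it says: "Non-TEAEs (pre-treatment and post-treatment) will be presented in the by patient data listings for the safety population". It names no AESI or secondary-malignancy table, rate or time-to-event summary. Protocol 11.2.5.1 has the same scope and adds: "Only treatment-emergent adverse events (TEAEs) will be collected". For study close, protocol 11.3 names only efficacy endpoints: final OS, PFS2 and the subsequent-therapy endpoints.

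**The concern.** Evaluating safety is a secondary objective. The protocol set up scheduled post-treatment contact that includes secondary malignancy, and it reports the drug as clastogenic in vitro (section 3.3.1.3). If the analysis text is followed as written, a malignancy first diagnosed more than 28 days after last dose has no denominator, no person-time and no comparison by arm. A by-patient listing cannot supply these.

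The window also depends on treatment. Dosing continues to progression and the design expects progression to come later on rucaparib, so crude TEAE percentages cover different lengths of time in the two arms. For late events that is not a like-for-like comparison, and the imbalance could mislead in either direction.

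Separately, the sentence in 11.2.5.1 on what is collected conflicts with four other protocol sections.

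**Working it through.** **1. Text side by side**

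| Item | Scheduled or required after last dose + 28 days | In a planned by-arm adverse-event table |
|---|---|---|
| Secondary malignancy | Yes, about every 12 weeks (5.1.5, Table 3, 9.4.3) | No |
| AESIs, any causality | Reportable, not scheduled (9.4.3, 9.5.4.1, 10.7, 10.8) | No |
| Safety summary at study close | – | None named (11.3) |

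**2. Inputs from the documents**
- Planning median PFS, ITT: 6 months on placebo, 8.5 on rucaparib (Protocol Table 4; SAP 2.3). Treatment runs to progression, so these stand in for time on drug.
- Allocation 2:1 in favour of rucaparib.
- Study period Q4 2013 to Q2 2022, about 102 months. Unblinding is dated April 2017 in protocol 11.3, about 41 months from the start (June 2017 in the synopsis and 5.4).

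**3. Check on the borrowed row.** With 378 events, HR 0.70, 2:1 allocation and one-sided 0.025: √(378 × 2/9) × |ln 0.70| = 9.165 × 0.3567 = 3.269. Then 3.269 − 1.960 = 1.309, which gives 90.5% power against 90% stated. The medians agree with the hazard ratio: 6/8.5 = 0.706.

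**4. Length of the tabulated window.** With exponential time on drug, the mean window is median/ln 2 + 28/30.4375 months.
- Placebo: 6/0.693 + 0.92 = 8.66 + 0.92 = 9.6 months.
- Rucaparib: 8.5/0.693 + 0.92 = 12.26 + 0.92 = 13.2 months.

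The ratio is 13.2/9.6 = 1.38. If a rare event had the same constant hazard in both arms, the tabulated percentage would be about 1.38 times as high on rucaparib from window length alone.

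**5. Share of follow-up outside the window.** Assumptions not in the documents: median OS of 24, 36 or 48 months, equal in both arms, and uniform accrual over 24 to 32 months. Time on treatment was simulated as exponential, followed by exponential post-progression survival scaled to the OS median. Follow-up was cut at 41 or 102 months from first entry, with arms weighted 1/3 and 2/3. Loss to follow-up and withdrawal were not modelled.

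| Median OS (months) | Outside at study close | Outside at April 2017 cut |
|---|---|---|
| 24 | 58% | 45-47% |
| 36 | 71% | 51-54% |
| 48 | 76-77% | 54-57% |

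Hand check (OS 36, 24-month accrual, study close): mean window (9.6 + 2 × 13.1)/3 = 11.9 months, mean follow-up (42.2 + 2 × 41.5)/3 = 41.7 months, and 1 − 11.9/41.7 = 71%.

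By arm at study close, 67-81% of placebo and 54-74% of rucaparib follow-up lies outside.

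**6. Sensitivity (28-month accrual).**
- The share passes one half at a median OS of about 20 months at study close and about 30 months at the 2017 cut.
- With the tBRCA medians (6 and 12 months) and OS of 24 to 48 months, it is 47-70% at study close and 37-48% at the 2017 cut.
- Counting only time beyond month 12, with the ITT medians, it is 77-90% and 68-77%.

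**The case against.** **Amendment timing.** The SAP was written to the original protocol and Amendments 1-3, for a cut-off set by the primary PFS event count. The protocol text in hand is post-Amendment 5 and does not show when secondary-malignancy monitoring or causality-independent late AESI reporting was introduced. This stands: a reader might infer that the SAP's authors had these data in view and set them aside, and the documents do not support that. It does not answer the point against current protocol 11.2.5.1 and 11.3, which leave the same gap.

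**Size.** A reader might infer that the tables omit most of the follow-up whatever one assumes, or a share as high as 65-84%. That upper range arises only if every patient is observed for a full 36 or 60 months, with no deaths or staggered entry. Sixty months could not have elapsed by 2017, and the documents give no survival figure. Only the conditional ranges above are defensible.

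**Ascertainment.** A reader might infer that late AESIs are actively sought until death. Scheduled contact is stated for secondary malignancy, survival and subsequent treatments; late AESIs are only reported. Follow-up also ends at loss, withdrawal or closure, and the same contacts serve OS.

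**Concealment.** Tabulating TEAEs and listing later events is common practice. Listings disclose the cases they hold, fatal cases count in OS by arm, and events of undeterminable onset are treated as TEAEs. Nothing suggests suppression. What remains is the absence of a summary.

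**Unseen sources.** The AESI list is in the Investigator's Brochure, and protocol section 10 does not name secondary malignancy. Whether every late case reaches the adverse-event dataset cannot be judged. SAP Appendices B and C are not shown, though SAP section 12 does not cite them.

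**Conclusion.** The point holds. Secondary malignancies and AESIs that arise after the TEAE window are followed or reportable, and no planned adverse-event count or rate by arm includes them. This follows from the text alone and is firmest against current protocol 11.2.5.1 and 11.3.

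The size is conditional. About 58-77% of follow-up lies outside the tables at study close and about 45-57% at the 2017 cut, given the ITT planning medians, median OS of 24 to 48 months and uniform accrual over 24 to 32 months. At the 2017 cut the fair description is roughly half. The expected window is about 3.6 months longer on rucaparib (13.2 − 9.6).

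The in vitro clastogenicity finding makes late events worth summarising, but the documents do not themselves link it to secondary malignancy. This is a cheap and worthwhile improvement to safety reporting. It does not affect the efficacy conclusions.

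**What to change.** - Add to protocol 11.2.5.1 and 11.3, and to the SAP for the final analysis, a by-arm table of secondary malignancies and one of AESIs, counted from first dose to last contact. Give number, percent and rate per 100 patient-years of follow-up.
- Split each table into on-treatment and post-treatment periods, and show subsequent anticancer therapy for post-treatment cases.
- Update both tables at the final OS analysis.
- Reconcile "Only treatment-emergent adverse events (TEAEs) will be collected" in 11.2.5.1 with sections 9.4.3, 9.5.4.1, 10.7 and 10.8.

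The cost is one or two tables from data already collected and one corrected sentence. Post-treatment cases will be partly attributable to later therapies, which the split makes visible. Because late AESIs are reported and not sought on a schedule, the post-treatment rates should be labelled descriptive.
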